6.1.4. Serious Adverse Events

6.1.4.1. Main Analysis

- Estimands: The percentage of participants reporting SAEs from vaccination to 1 month after vaccination ([Section 2.2](#)).
- Analysis set: Safety population ([Section 4](#)).
- Analysis time point: Vaccination to 1 month after vaccination.
- Analysis methodology: Descriptive statistics.
- Reporting results: The numerator (n) and the denominator (N) used in the percentage calculation, the percentage (%), and the corresponding 2-sided 95% CI for participants reporting any SAEs, by system organ class and each preferred term within system organ class, will be presented.

6.1.4.2. Supplementary Analyses

All SAEs will be noted in the AE listings. SAEs will also be displayed in a separate listing.

6.2. Secondary Endpoint

6.2.1. OPA Titers

[figure not shown]
6.2.1.1. Main Analysis

- Estimand: GMFRs of pneumococcal serotype-specific OPA titers from before to 1 month after vaccination (by age cohort) ([Section 2.2](#)).
- Analysis set: Evaluable immunogenicity population ([Section 4](#)).
- Analysis time points: Before vaccination and 1 month after vaccination.
- Analysis methodology: The GMFR and corresponding 2-sided 95% CI will be calculated as described in [Section 5.2.4](#).
- Reporting results: For each of the serotypes, the GMFRs and the corresponding 2-sided 95% CIs will be presented at the specified time points.

CCI

CCI

6.4. Subset Analyses

Not applicable.

6.5. Baseline and Other Summaries and Analyses

6.5.1. Baseline Summaries

6.5.1.1. Demographic Characteristics

Demographic characteristics, including age at vaccination, sex, race, ethnicity, height, weight, and racial designation, will be summarized for the evaluable immunogenicity population and safety population.

6.5.1.2. Medical History

Each reported medical history term will be mapped to a system organ class and preferred term according to MedDRA. The number and percentage of participants with an assigned vaccine having at least 1 diagnosis, overall and at each system organ class and preferred term level, will be summarized for the safety population.

6.5.2. Study Conduct and Participant Disposition

6.5.2.1. Participant Disposition

Disposition of participants relative to vaccination will be summarized for all participants as follows: The number and percentage of participants who receive vaccination, complete the 1-month postvaccination visit, and withdraw between vaccination and the 1-month post vaccination visit with specific reasons (participant request, lost to follow-up, AE, protocol violation, other) will be summarized by cohort and overall.

Participants excluded from the safety population will also be summarized along with the reasons for exclusion.

6.5.2.2. Blood Samples for Assay

The number and percentage of enrolled participants providing blood samples within and outside of protocol-specified time frames will be tabulated.

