1.3. Schedule of Activities

The SoA table provides an overview of the protocol visits and procedures. Refer to the **STUDY ASSESSMENTS AND PROCEDURES** section of the protocol for detailed information on each procedure and assessment required for compliance with the protocol.

The investigator may schedule visits (unplanned visits) in addition to those listed in the SoA table, in order to conduct evaluations or assessments required to protect the well-being of the participant.

Visit Number	1	2
Visit ID	Vaccination	Follow-Up Visit
Visit Window (Days)	Day 1	28 to 42 Days After Visit 1
Visit Type	Clinic Visit	Clinic Visit
Obtain informed consent	X	
Assign participant number via IRT	X	
Obtain demography and medical history data	X	
Measure height and weight	X	
Perform clinical assessment ^a	X	
Review prior vaccination history to confirm participants are naïve to pneumococcal vaccines	X	
Record concomitant nonstudy vaccinations and concomitant medications used for treatment of SAEs	X	X
Obtain prevaccination oral temperature	X	
Perform pregnancy test (if appropriate)	X	
Contraception check (if appropriate)	X	
Review inclusion and exclusion criteria	X	
Obtain blood sample for immunogenicity assessment of OPA titers (~30 mL) ^b	X ^c	X
Administer study intervention	X	
Observe and record acute reactions for 30 minutes after 20vPnC administration	X	
Provide participant with an e-diary (device or application, if used), digital thermometer, and measuring device and instruct to collect prompted local reactions and systemic events for 7 days after vaccination	X	
Provide a participant contact card	X	
Review e-diary data (daily is optimal during 7-day diary period)	X-----X	

Visit Number	1	2
Visit ID	Vaccination	Follow-Up Visit
Visit Window (Days)	Day 1	28 to 42 Days After Visit 1
Visit Type	Clinic Visit	Clinic Visit
Review e-diary symptoms with participant and obtain stop dates where applicable		X
Collect e-diary or assist the participant to delete the application, if applicable		X
AEs and SAEs collection	X-----X	

Abbreviation: IRT = interactive response technology

- a. Including, if indicated, a physical examination.
- b. Immunogenicity subset only: Blood will be drawn in the first approximately 50 participants in each age cohort (18 to 49 years of age and \geq 50 years of age) for a study total of approximately 100 participants (approximately 25% of all participants).
- c. Blood sample will be collected prior to vaccination.

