2.3. Study Design

This Phase 3, single-arm, multicenter study will be conducted at investigator sites in India. The purpose of this study is to assess the safety and immunogenicity of 20vPnC in adults ≥ 18 years of age.

Approximately 400 eligible adults ≥ 18 years of age will be vaccinated with 20vPnC.

Participants will be assigned to 2 cohorts by age (approximately 200 participants per cohort): 18 to 49 years of age and ≥ 50 years of age. The first 50 participants in each age cohort will be enrolled in the immunogenicity subset (with a study total of 100 participants). Participants in the immunogenicity subset will have blood drawn for immunogenicity assessments prior to vaccination and at approximately 1 month after vaccination (blood will be drawn in the first approximately 50 participants in each age cohort [18 to 49 years of age and ≥ 50 years of age] for a study total of approximately 100 participants [approximately 25% of all participants]). The 20vPnC will be prepared and administered by an appropriately qualified investigator site staff member. Participants will be observed for 30 minutes after vaccination, and any reactions occurring during that time will be recorded as AEs.

Each participant will participate in the study for approximately 1 month. Based on an estimated enrollment timing, the study duration will be approximately 4 months.

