4. ANALYSIS SETS (POPULATIONS FOR ANALYSIS)

Analysis populations are defined for the statistical analysis of safety results in the table below.

Population	Description
Enrolled in the study	All participants who signed an ICD.
Assigned to study intervention	All participants who are assigned an enrollment number in the IWR system.
Safety	All participants who receive any study intervention and have safety data assessed after vaccination.
Evaluable immunogenicity	All eligible participants in the immunogenicity subset who receive 1 dose of the study intervention with at least 1 valid immunogenicity result from the blood sample collection within 27 to 49 days after vaccination and have no other major protocol deviations as determined by the clinician.
CCI	

E-diary data will be summarized among those in the safety population who report any e-diary data.

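### Does the blood-sample table's base of enrolled participants, with clinician-judged exclusions, conceal losses from the GMFR analysis?

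*SAP*

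**What the plan says.** SAP 6.5.2.2 consists of one sentence: "The number and percentage of enrolled participants providing blood samples within and outside of protocol-specified time frames will be tabulated". It names no denominator outright and no split by cohort or visit. SAP 4 defines the set of those enrolled in the study as "All participants who signed an ICD".

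Blood is taken only from a subset. Protocol 1.3, footnote b, has "Immunogenicity subset only: Blood will be drawn in the first approximately 50 participants in each age cohort", before vaccination and again at Visit 2. SAP 2.3 plans: "Approximately 400 eligible adults ≥ 18 years of age will be vaccinated with 20vPnC". It then describes the subset: "The first 50 participants in each age cohort will be enrolled in the immunogenicity subset (with a study total of 100 participants".

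The GMFR is computed in the evaluable immunogenicity population (SAP 6.2.1.1). SAP 4 requires of that population a valid result from a sample taken "within 27 to 49 days after vaccination and have no other major protocol deviations as determined by the clinician". The visit window in Protocol 1.3 is 28 to 42 days. On exclusions, SAP 6.5.2.1 states: "Participants excluded from the safety population will also be summarized along with the reasons for exclusion". The readable text has no matching sentence for the evaluable immunogenicity population.

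**The concern.** Four features of the SAP raise the question.

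- **Denominator.** With the defined meaning of enrolled, the percentage giving blood is capped near one quarter and hardly moves when samples are lost, so it says little about compliance.
- **Windows.** A sample taken 46 days after vaccination is outside the protocol time frame in this table, yet admissible for the GMFR.
- **Reasons.** Exclusions with reasons are promised for the safety population only.
- **Judgement.** Membership of the GMFR set depends partly on a clinician's view of what counts as a major deviation. The readable text does not say that this view is recorded before the opsonophagocytic activity (OPA) titers are released.

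The GMFR is the only immunogenicity estimand not redacted, and it rests on about 50 people per cohort. Selective loss could shift it. If the outputs also concealed that loss, a reader could not judge the result.

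**Working it through.** **The plan's own figure.** SAP 2.3 gives the subset as "for a study total of approximately 100 participants [approximately 25% of all participants". Check: 100/400 = 25.0%, which agrees.

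**Effect of the literal denominator.** Inputs are about 400 vaccinated and about 100 bled (SAP 2.3). With L subset members lacking a valid Visit 2 sample, the literal percentage is (100 − L)/400 and the informative one is (100 − L)/100.

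| L | Count shown | Over 400 | Over 100 |
|---|---|---|---|
| 0 | 100 | 25.0% | 100% |
| 5 | 95 | 23.8% | 95% |
| 10 | 90 | 22.5% | 90% |
| 20 | 80 | 20.0% | 80% |

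If 440 people signed consent (an assumption, to allow for screen failures), complete sampling would read 100/440 = 22.7%. The percentage column is weak, but the count column shows the loss in every row.

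**What else shows the loss.**

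- SAP 6.5.1.1 summarizes demographics for the evaluable immunogenicity population, which gives its size.
- SAP 5.2 lists n among the standard statistics and requires immunogenicity results by age cohort.
- SAP 6.5.2.1 reports withdrawals before the one-month visit, with reasons, by cohort and overall.
- Subset members are bled before vaccination, so the count of Visit 1 samples shows how many entered the subset.

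What the readable text lacks is a reason-by-reason breakdown of exclusions from the evaluable set.

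**Which meaning of enrolled?** SAP 4 gives the consent-based one. SAP 2.3 also speaks of people being enrolled in the immunogenicity subset. Where the SAP fixes a denominator expressly, as in 6.5.3.1, it says so; 6.5.2.2 does not. A programmer tabulating samples due from about 100 people has an obvious sensible base.

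**The two windows.** Days 28 to 42 describe adherence to the visit schedule. Days 27 to 49 describe eligibility for analysis, which Protocol 9.2 left open and the SAP then settled. The second interval contains the first. A 46-day sample is late for the visit and still usable, and the two outputs report two different facts.

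**Worst case for selective exclusion.** Assume n = 50, normal ln fold rises with SD 1.0, 1.5 or 2.0 (not from the documents), and deliberate removal of the k lowest values. The inflation figures come from 40,000 simulated samples. The last column is exp(t × SD/√50) − 1 with t = 2.01 on 49 degrees of freedom.

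| SD | GMFR, k = 3 | GMFR, k = 5 | Upper 95% limit above GMFR |
|---|---|---|---|
| 1.0 | +13% | +21% | +33% |
| 1.5 | +20% | +33% | +53% |
| 2.0 | +28% | +46% | +77% |

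Excluding a person removes that person's results for all 20 serotypes. If the three are the lowest on one serotype and the correlation between serotypes is 0.3 to 0.6 (assumed), the 20% at SD 1.5 becomes, for the other 19, exp(0.3 × ln 1.20) − 1 = 6% to exp(0.6 × ln 1.20) − 1 = 12%.

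**The case for a change.** The strongest contrary case is that defined terms should mean what they are defined to mean. A programmer who follows SAP 4 divides by about 400 or more and produces a percentage of little use. The neighbouring sections 6.5.2.3 and 6.5.3.1 do name their base. The subset is only approximately 50 per cohort, so the count has no fixed comparator printed beside it. The disposition table covers all participants in a cohort and does not isolate the subset. In a single-arm trial treatment blinding offers no protection, and neither coded laboratory samples (Protocol 8.1.1) nor a SAP finalized before analysis (Protocol 9.3) fixes who is excluded.

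Much of this stands as description: the wording is loose, and the readable text gives neither a list of major deviations nor a time for deciding them. It does not stand as evidence of concealment or bias. The Visit 1 sample count supplies the missing comparator. Knowing that everyone received 20vPnC tells a clinician nothing about who responded. Only access to titers could steer exclusions, and no section describes such access. A redacted row follows the evaluable set in both analysis-set tables, and redacted text follows the statement that the analysis is primarily based on that set. A further immunogenicity population or analysis may therefore exist, and its absence cannot be asserted.

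That the worst-case inflation lies within the sampling uncertainty would not excuse a real bias. It does show the scale of a scenario for which the documents give no support.

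**Conclusion.** No change to the plan is called for. The denominator in SAP 6.5.2.2 is a wording slip in a study-conduct table. Taken literally it turns 90% into 22.5%, but the accompanying count of 90 is unaffected and the size of the evaluable set is reported elsewhere. The two windows are compatible. A table of reasons for exclusion from the evaluable set, and the timing of deviation decisions, are details that analysts would be expected to settle sensibly before analysis.

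The trial is descriptive, with no hypothesis, margin or success rule to tip. The GMFR formula, the analysis set, the confidence interval and the sample size are the same whichever base the table uses. The 13% to 46% inflation requires deliberate removal of the lowest responders and assumed SDs of 1.0 to 2.0 on the natural-log scale.

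This conclusion assumes that the counts are shown by visit, as the plural time frames and the two scheduled draws suggest, and that deviation decisions are made without sight of titers, which the readable text neither states nor contradicts.

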6.5.2.3. E-Diaries

The participants who were vaccinated and who transmitted e-diaries will be summarized. The summary will also include the number and percentage of vaccinated participants not transmitting the e-diary, transmitting the e-diary, and transmitting the e-diary for any day in the required reporting period, by cohort and overall.

The safety population will be used.

6.5.3. Study Intervention Exposure

6.5.3.1. Vaccination Timing and Administration

The number and percentage of participants enrolled and receiving the vaccine (20vPnC) within the protocol-specified time frame, as well as before and after the specified time frame, will be tabulated for each cohort for all participants. The denominator for the percentage is the total number of participants in the given cohort.

6.5.4. Concomitant Medications and Nondrug Treatments

Each concomitant vaccine will be summarized according to the ATC fourth-level classification. The number and percentage of enrolled participants receiving concomitant vaccines will be summarized by cohort and overall.

Concomitant medications used to treat SAEs will be summarized for the time of vaccination to 1 month after vaccination by cohort (safety population) and overall.

6.6. Safety Summaries and Analyses

Summaries and analyses of the safety measures, including local reactions, systemic events, AEs, and SAEs, are described in the section for the primary endpoints (see [Section 6.1](#)).

7. INTERIM ANALYSES

7.1. Introduction

Not applicable.

7.2. Interim Analyses and Summaries

Not applicable.

